Rationale	
Open questions are still needed to be answered:
 
 - In the exclusive radiotherapy scenario, does ENI produce an overall or biochemical relapse free survival advantage over prostate only radiotherapy for intermediate/high/very high-risk cases? - If ADT is added to prostate only radiotherapy, in intermediate/high/very high-risk cases, ENI is any longer needed?

	
 - Is ENI, associated or not to ADT, linked with an OS or bRFS survival advantage in patients submitted to adjuvant postsurgical prostate radiotherapy? - Additional toxicity due to the larger volumes treated might be reduced by more sophisticated radiotherapy techniques when ENI is added to prostate? - How many Radiation Oncology centers use ENI to treat patients with intermediate/high/very high-risk prostate cancer, with or without ADT? - The data obtained from the present observational study will be helpful for designing a subsequent randomized controlled trial.
End-points	
Primary:
 
 - Overall survival; 
Secondary:
 
 - Cause-specific (CSS) and Biochemical Relapse Free survival (bRFS); - acute and late toxicity evaluation (rectal, bladder, bowel toxicity, according to CTCAE v.4 scale); - Quality of Life deterioration (according to the UCLA-PCI scale).
Study design	
This is a prospective, multicenter, observational cohort study aimed to describe the advantage/disadvantage of different treatments of patients with intermediate/high/very high risk prostate cancer, through a web-based database.
 
The study will include all consecutive patients affected by intermediate, high or very high-risk prostate cancer that fit to the inclusion criteria and who are evaluated at each Centre involved in the study. Patients may have already undergone or not to radical prostatectomy and/or pelvic lymphadenectomy.
 
Phase 1: Establishment of the network of Centers involved in the study Phase 2: Activation and recruitment of eligible cases Phase 3: Follow-up (1,3,6,12/18,24/30/36 months)

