Visits and exams	
Every prostate cancer patient consecutively evaluated at the recruiting Centers and planned to receive radical exclusive or post-operative radiotherapy will be registered; this registration includes demographic and staging results data.
 
Only intermediate, high, very high patients will have, however, treatment and follow up CRF compiled, based on the inclusion criteria
 
Eligible patients will then receive all the information necessary to formulate their adhesion to the study and finally the physician will fill in the “Pretreatment” CRF that will include: Demographic Information; Anamnestic data; Initial diagnosis (date; PSA at diagnosis); Risk factors; Staging; Quality of life and symptoms caused by prostate cancer; General quality of life;
 
The choice of the treatment will be done based on commonly used international guidelines and on the specific internal protocol of each participating Center.
 
Since this study is observational, involved patients will be treated following good clinical practice and institutional policies procedures.
 
Clinical outcomes and variables, demographic features, dosimetric analysis and acute/late toxicities of both RT (with and without ENI) and ADT will be reported.

	
Follow-up visits on 1,3,6,12/18,24/30 and 36 months
 
Every patient will be contacted by the physicians to fill a CRF that will include: Vital state (mortality, date and causes of death) or loss to follow up; Last PSA value; Other treatments (drugs); type of RT and ADT treatment Acute and late toxicities; Biochemical Relapse with PSA value and date of last PSA; Quality of life and symptoms due to prostate cancer; General quality of life.
 
Survival status (mortality, date and cause of death) or exit from the study; If macroscopical recurrence or disease progression will occur, the radiological exams (if performed) will be reported; Further treatments received/planned after radiotherapy; The last available PSA;
 
Acute/Late toxicity
 
Genitourinary and gastrointestinal toxicity due to radiation therapy.
 
A CRF will be completed regarding: Technical characteristics of the radiation treatment; Quality of life and complications due to prostate cancer; General quality of life

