In the adjuvant setting, sterilizing microscopic disease potentially persistent after radical surgery, particularly in high-risk patients, represents the rationale of adding WPRT to prostatic bed radiotherapy in pN0 patients. Goldner et al. evaluated the clinical impact of prostate only adjuvant RT in pN0 patients showing a 5-year biochemical relapse free survival of 100% and 58% in patients with a risk of nodal involvement <15% and >15%, respectively. These findings may be explained by a microscopic involvement of pelvic structures (lymph nodes, bone) other than prostate bed. However, the role of adjuvant post-surgical WPRT need to be validated by large prospective studies, not actually ongoing to our knowledge. [37, 38, 39, 40]. Moreover, no clear-cut guidelines are available about the usefulness of adding ADT to adjuvant RT in the different subsets of pN0 patients.

On the other hand, nodal involvement (pN1) is a strong negative prognostic factor and adjuvant RT in these patients may be useful to optimize loco-regional control deferring first or second line systemic therapies [41]. Actually, the standard adjuvant treatment for pN1 PCa patients is represented by long term ADT, but the association with WPRT might significantly increase survival outcomes [42]. A recent analysis conducted by SEER on “pN1 M0” PCa patients treated with adjuvant WPRT seems to confirm the benefit obtained by the association of WPRT with ADT, demonstrating a survival advantage for intermediate risk patients [43].

Conclusions, rationale and summary of the study

In conclusion, open questions about ENI for prostate cancer still remain:

1. In the exclusive radiotherapy scenario, does ENI produce an overall or biochemical relapse free survival advantage over prostate only radiotherapy for intermediate/high/very high risk cases?
2. If ADT is added to prostate only radiotherapy, in intermediate/high/very high risk cases, ENI is any longer needed?

3. Is ENI, associated or not to ADT, linked with an OS or bRFS survival advantage in patients submitted to adjuvant postsurgical prostate radiotherapy?
4. Additional toxicity due to the larger volumes treated might be reduced by more sophisticated radiotherapy techniques when ENI is added to prostate?
5. How many Radiation Oncology centers use ENI to treat patients with intermediate/high/very high-risk prostate cancer, with or without ADT?

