In summary, the study aims at the definition of survival, toxicity and QoL data in a representative sample of intermediate, high and very high risk prostate cancer patients consecutively recruited in Italian Radiation Oncology Centres over two years. Parameters considered will be OS, CSS and bRFS, toxicity (rectal, bladder, bowel toxicity, according to CTCAE v.4 scale) and QoL (according to the SF-12 scale and UCLA-PCI scale). Primary end point will be OS. Secondary endpoints will be CSS, bRFS, gastrointestinal and genitourinary toxicity, QoL deterioration.

Study Design

This is a prospective, multicenter, observational cohort study aimed to describe the advantage/disadvantage of different treatments of patients with intermediate/high/very high risk prostate cancer, through a web-based database.

Study Duration

The recruitment period, taking into account the needed sample size (*v.infra*) will be of two years, followed by three-year follow up period for each patient, with an accrual of at least 400-500 patients.

Population, Procedures

The study will include all consecutive patients affected by intermediate, high or very high-risk prostate cancer that fit the inclusion criteria and who are evaluated at each Centre involved in the study. Patients may have already undergone or not to radical prostatectomy and/or pelvic lymphadenectomy.

Inclusion criteria

- Men older than or aged 18 years;
- Histologically confirmed intermediate, high or very high risk prostate cancer patients (NCCN classification: Intermediate Risk T2b and T2c or Gleason Score 7 or PSA value between 10 and 20 ng/mL; High risk: T3a or Gleason score 8-10 or PSA > 20 ng/ml; Very high risk: T3b-T4 or patients with multiple adverse risk factors reported in the high risk category that may be shifted in the very high risk group
- Patients eligible for -and actually submitted to- radical radiotherapy treatment (+/- androgen deprivation) or adjuvant radiotherapy treatment after surgery (radical prostatectomy +/- pelvic lymphadenectomy);
- No other synchronous or previous malignant tumor other than skin basal cell carcinoma;
- Patients able to understand and sign the appropriate informed consent;
- Patients able to fill the QoL questionnaire;

Exclusion criteria

- Patients aged less than 18;

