Centers involved will identify all the eligible cases with biopsy proven prostate adenocarcinoma. Patients who are candidate to get involved in the study will be contacted by the physician in charge of the study for each Center. **Every** prostate cancer patient consecutively evaluated at the recruiting Centers and planned to receive radical exclusive or post-operative radiotherapy will be registered; this registration includes demographic and staging results data; only intermediate, high, very high patients will have, however, treatment and follow up CRF compiled (both treated with or without ENI; +/- ADT).

Eligible patients will then receive all the information necessary to formulate their adhesion to the study and finally the physician will fill in the “Pretreatment” Case Report Form (CRF) that will include:

- Demographic Information (date of birth, study title, civil state, working information);
- Another person (relatives, friends,...) as a contact to minimize follow up loss;
- Anamnestic data (height, weight, smoking habit, comorbidities, Cumulative Illness Rating Scale [44], Attachment 1);
- Initial diagnosis (date; PSA at diagnosis);
- Risk factors;
- Staging (clinical TNM, date of biopsy, Gleason score, total number of samples, number of positive samples);
- Quality of life and symptoms caused by prostate cancer (using Italian UCLA Prostate Cancer Index) [45, 46];
- General quality of life (SF-12 Standard V1) [47].

The choice of the treatment will be done based on commonly used international guidelines and on the specific internal protocol of each participating Center.

Since this study is observational, involved patients will be treated following *good clinical practice* and institutional policies procedures.

Clinical outcomes, (such as overall survival and biochemical relapse free survival) and variables, demographic features, dosimetric analysis and acute/late toxicities of both RT and ADT will be reported.

Phase 3: Follow-up (1, 3, 6, 12, 18, 24, 30, 36 months)

After the end of the radiotherapy treatment patients will be evaluated 1, 3, 6, 12, 18, 24, 30 and 36 months since the last session.

Every patient will be contacted by the physicians to fill a CRF that will include:

- Vital state (mortality, date and causes of death) or loss to follow up;
- Last PSA value;

- Other treatments (drugs);

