In order to describe the data, mean and standard deviation will be used for normally distributed continuous variables, median and ranges for non-normally distributed continuous variables, proportions and percentages for categorical variables. Associations between two categorical variables will be assessed through the Pearson's chi-squared test or Fisher test, when appropriate. Differences between two-sample central tendencies will be assessed with a two independent sample t-test or Mann-Whitney U test or Wilcoxon, depending on distribution of the continuous variable.

Analysis of variance and covariance and regression models will be used for evaluating the associations of some variables with survival taking account of possible confounders.

In order to compare groups in terms of survival end-points, Kaplan-Meier curves will be estimated and log-rank tests will be performed.

Periodical analyses are planned in order to check the quality of entered data.

The analyses will be performed by using STATA 13 (StataCorp. 2013. Stata Statistical Software: Release 13. College Station, TX: StataCorp LP) or SPSS Statistical Software.

Ethical committee

After the final approval by the AIRO-PCSG, the Protocol will be submitted to the Ethical Committee (EC) of the Study Coordinating Centre; when it will be approved, the single participating Centres will consequently apply for approval of their EC. According to the judgment of the PI and of the Study Coordinator, the first patient will be enrolled when a sufficient number of Centres will have obtained EC approval. This will be the starting date for the study.

The present study will be performed in accordance with the present protocol, with the principles of Good Clinical Practice in the respect of the ICH GCP guidelines and the ethical principles contained in the Helsinki declaration.

Publication rules

Interim and final results of the study will be published under the final responsibility of the PI and of the Study Coordinator.

The following publication rules will be enforced:

1. The participating Centers should approve the paper;
2. Only Centers contributing to more than 5% of the cases collected will have a person quoted as Author of the paper; however, every Center contributing to the common database, as well as the people working to realize the Study, will be publicly quoted and their contribution acknowledged in the paper;
3. Authorship is granted in proportion to:
 - a. the cases contributed to the database;

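### Confounder adjustment is planned for survival only, so a toxicity contrast by ENI status made under the plan as written would be unadjusted and may be confounded

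*Combined protocol and SAP*

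**What the plan says.** The synopsis lists among the secondary end-points "acute and late toxicity evaluation (rectal, bladder, bowel toxicity, according to CTCAE v.4 scale").

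Statistical Analyses (same text in the synopsis and the body) contains these methods:

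- Adjusted: analysis of variance and covariance, and "regression models will be used for evaluating the associations of some variables with survival taking account of possible confounders".
- Categorical data: "Associations between two categorical variables will be assessed through the Pearson's chi-squared test or Fisher test, when appropriate".
- Continuous data: "Differences between two-sample central tendencies will be assessed with a two independent sample t-test or Mann-Whitney U test or Wilcoxon", depending on the distribution.
- Survival end-points: Kaplan-Meier curves and log-rank tests.

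Neither document section mentions a covariate model, stratification, matching, a propensity score or a centre effect for toxicity.

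On what will be reported, Study Design describes a cohort "aimed to describe the advantage/disadvantage of different treatments of patients with intermediate/high/very high risk prostate cancer", and the synopsis (Visits and exams) states that "dosimetric analysis and acute/late toxicities of both RT (with and without ENI) and ADT will be reported". Treatment is chosen "based on commonly used international guidelines and on the specific internal protocol of each participating Center" (Phase 2).

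**The concern.** The plan accepts that survival comparisons need adjustment. The same treatment choices determine who could have which toxicity, yet the adjustment sentence stops at survival. An analyst who follows the text would tabulate toxicity by ENI status and apply a crude test.

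Such a table could mix an effect of ENI with differences in surgical setting, patient characteristics or centre. That matters because the study asks whether better technique can limit the added toxicity of larger volumes (question 4 of the rationale), and because its data are meant to help design a randomised trial (aims 6 and 7).

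**Working it through.** **1. Match of methods to endpoint.** Toxicity on the forms is a grade (G0 to G4) or a yes/no item. The listed methods that fit are chi-squared or Fisher for occurrence and Mann-Whitney for grade. All are unadjusted. The adjusted models are tied to survival by the wording of the sentence.

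**2. Routes to confounding in the documents.**

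- *Setting.* Radical and post-operative patients are in one cohort. The Background associates surgery with incontinence and bleeding before radiotherapy.
- *Patient mix.* The Background gives the reason for pelvic treatment after surgery: eradicating residual microscopic disease, "particularly in high-risk patients, represents the rationale of adding WPRT to prostatic bed radiotherapy in pN0 patients". It also discusses pelvic treatment for pN1 men. ENI use may therefore follow risk and nodal status.
- *Centre.* Each of the 15-20 expected centres applies its own protocol, so ENI use may cluster by centre.
- *Baseline symptoms.* Attachment 1 shows no baseline toxicity grade. In Attachment 2 only impotence and incontinence are coded as present before or after radiotherapy. Toxicity is to be recorded as that caused by radiotherapy, which removes pre-existing symptoms only in part.

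**3. The plan's own figure.** There is none for toxicity. The one precision statement concerns 5-year overall survival and reproduces: 0.8 ± 1.96 × √(0.8 × 0.2/400) = 0.8 ± 0.039, or 0.761 to 0.839, against the stated 0.76-0.84.

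**4. Illustration on assumed rates.** The documents give no toxicity rates and no ENI shares. Assume N = 400, two equal strata (for example two settings or two kinds of centre), toxicity risks a and b, ENI shares e and f with e + f = 1, and no effect of ENI within a stratum. Then

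- crude risk with ENI = e·a + f·b
- crude risk without ENI = (1 − e)·a + (1 − f)·b

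For a = 10%, b = 20%, e = 40%, f = 60%: 0.04 + 0.12 = 0.16 against 0.06 + 0.08 = 0.14. The crude odds ratio is (0.16/0.84)/(0.14/0.86) = 1.17. The last column is the approximate share of studies in which an unadjusted 5% test would reject (normal approximation, 200 per group).

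| Toxicity in strata | ENI use in strata | Risk with / without ENI | Crude OR | Rejects |
|---|---|---|---|---|
| 10% / 20% | 40% / 60% | 0.16 / 0.14 | 1.17 | 8% |
| 10% / 20% | 30% / 70% | 0.17 / 0.13 | 1.37 | 20% |
| 10% / 20% | 20% / 80% | 0.18 / 0.12 | 1.61 | 39% |
| 20% / 30% | 40% / 60% | 0.26 / 0.24 | 1.11 | 7% |
| 20% / 30% | 30% / 70% | 0.27 / 0.23 | 1.24 | 15% |
| 20% / 30% | 20% / 80% | 0.28 / 0.22 | 1.38 | 28% |

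If ENI is commoner in the low-toxicity stratum, the odds ratios invert (1.17 becomes 0.85). If ENI use is balanced, there is no bias.

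**5. Scale against chance.** At 20% risk and 200 men per group, SE(log RR) = √(2 × 0.8/(0.2 × 200)) = 0.20, so a 95% interval spans a factor of exp(1.96 × 0.20) = 1.48 each way. The mild imbalances above are well inside that.

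**The case against.** The strongest reply is that the plan does not commit to this contrast. No test of toxicity between ENI and non-ENI men is named. Aim 4 registers toxicity in men who receive pelvic irradiation, aim 5 compares subgroups with historical data, and question 4 concerns technique. The phrase about reporting with and without ENI stands in the synopsis; the matching sentence in Phase 2 omits it. This stands, and a reader should not infer that the plan pre-specifies a biased test. What remains is that Phase 2 has follow-up forms completed for men treated with or without ENI, the synopsis says toxicity will be reported for both, and the plan supplies only crude tools for doing so.

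Second, the documents do not complete a patient-level link. They tie pelvic treatment to oncological risk and pN1 disease, but not those factors to toxicity. They tie surgery to urinary symptoms, but not to ENI use, and they suggest that men with severe post-surgical effects may wait for salvage treatment instead. This also stands. A reader might infer that the crude contrast must overstate ENI toxicity; the documents support neither that direction nor any amount.

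Third, analysis of covariance is an unusual choice for censored survival, so the sentence may simply be loosely drafted. That is possible, and it is a reason for a short correction. Left as it is, covariates and the handling of centre would be chosen after the data are seen.

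**Conclusion.** The point holds as a gap in the written analysis: adjustment is confined to survival, and an ENI contrast in toxicity made under the plan as written may be confounded by setting, patient mix and centre. It is a cheap improvement for a secondary endpoint.

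The conclusion rests on the text of Statistical Analyses, the non-random choice of treatment and the mixed cohort. It does not rest on the illustration, whose crude odds ratios of 1.11 to 1.61 under no effect follow from assumed rates and could equally fall below 1. Nor should it be read as a failure of data capture: most of the factors needed are already collected. Adjustment would reduce confounding by recorded factors and would not remove it all.

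**What to change.** Add after the existing adjustment sentence in Statistical Analyses:

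> Regression models taking account of possible confounders will also be used for any comparison of acute and late grade 2+ toxicity between men treated with and without ENI (any pelvic or nodal target in V1-V3). They will adjust for age, CIRS, smoking, risk group, nodal status, surgical setting with or without lymphadenectomy, neoadjuvant ADT, and the baseline UCLA-PCI urinary or bowel score, and will account for centre. Chi-squared and Fisher results are descriptive. The number of covariates will be limited by the number of events. The report will state how many centres gave ENI to all or to none of their patients.

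These factors are on Attachment 1 or can be derived from it, except neoadjuvant ADT and the target volumes, which are on Attachment 2. No new data are needed. Nodal status belongs in the list because the target-volume definition also captures node-positive men. The choice of centre method, and any analysis within technique, can be left to the statistician.

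Costs and limits:

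- *Events.* The full list is about 12 parameters before centre: ENI, age, CIRS, smoking (2), risk group (2), nodal status, setting, lymphadenectomy, neoadjuvant ADT, baseline score. At assumed event rates of 10%, 20% or 30% in 400-500 men there are 40-50, 80-100 or 120-150 events, or about 3-4, 7-8 or 10-12.5 per parameter. With few events the list must be cut or penalised.
- *Precision.* Intervals widen once centre is accounted for, by an amount that depends on how strongly ENI use clusters. If the log-odds of ENI use vary normally between centres with an assumed SD of 1.5, 3 or 4 around 50% use, the mean within-centre variance of ENI use is 0.177, 0.115 or 0.091. Using only within-centre information then multiplies the standard error by about √(0.25/0.177) = 1.19, √(0.25/0.115) = 1.47 or √(0.25/0.091) = 1.66.
- *Scope.* Late grades on the forms cover proctitis and cystitis only, and UCLA-PCI urinary items mainly measure leakage, so baseline urinary symptoms are only partly captured.

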Statistical considerations	
Sample size
 
From previous experiences of the AIRO Prostate Cancer Study Group (AIRO PCSG), at least 15-20 Radiotherapy Centers from different regions of the country will be able to participate to the study. It is conceivable an accrual of at least 400-500 patients within 2 years and a further follow up of at least 3 years for each patient. For intermediate and high risk patients, an overall survival at 5 years of 0.8 has been previously reported (RTOG 94-13). According to the primary end-point of the study, a sample size of 400 patients will allow to estimate a 5-year survival of 0.8 with 95% confidence interval of 0.76-0.84.
 
Statistical Analyses
 
In order to describe the data, mean and standard deviation will be used for normally distributed continuous variables, median and ranges for non-normally distributed continuous variables, proportions and percentages for

	
categorical variables. Associations between two categorical variables will be assessed through the Pearson's chi-squared test or Fisher test, when appropriate. Differences between two-sample central tendencies will be assessed with a two independent sample t-test or Mann-Whitney U test or Wilcoxon, depending on distribution of the continuous variable.
 
Analysis of variance and covariance and regression models will be used for evaluating the associations of some variables with survival taking account of possible confounders.
 
In order to compare groups in terms of survival end-points, Kaplan-Meier curves will be estimated and log-rank tests will be performed.
 
Periodical analyses are planned in order to check the quality of entered data. The analyses will be performed by using STATA 13 (StataCorp. 2013. Stata Statistical Software: Release 13. College Station, TX: StataCorp LP) or SPSS Statistical Software.

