We propose a no-profit, multicenter observational study to collect data of consecutive patients treated with ENI both in the exclusive radical radiotherapy scenario and in the adjuvant postsurgical setting. Cases treated both with and without associated ADT will be recruited to evaluate Overall survival (OS) (that will be the main endpoint), Cause-specific (CSS) and Biochemical Relapse Free survival (bRFS), toxicity and Quality of Life (QoL) (the secondary endpoints).

Aims of the study

Clinical features and outcomes will be assessed as better detailed in the following lines:

1. To define the diffusion of the practice of treating pelvic lymph-nodes in patients affected by intermediate/high/very high risk non-metastatic prostate cancer (PCa) among Italian Radiation Oncology Centres, submitted to radical or post-operative radiotherapy;
2. To define the diffusion of the different radiotherapy techniques used to treat pelvic nodes and the other features of the radiation treatment;
3. To register prospectively biochemical and clinical failure, prostate cancer deaths and deaths for any cause in the population studied;
4. To register prospectively the toxicity due to radiotherapy and androgen deprivation therapy in patients treated with pelvic nodes radiotherapy;
5. To compare clinical outcomes and toxicities observed in the different clinical and therapeutic subgroups with the corresponding historical data relative to PCa patients treated with radiotherapy with or without elective pelvic nodal irradiation, already available in the existing AIRO (Italian Society of Radiation Oncology) databases;

6. To exploit the collected data to define the need and the features of a prospective randomized trial evaluating the efficacy of elective pelvic nodal irradiation in patients with intermediate/high/very high risk non-metastatic prostate cancer.
7. The data obtained from the present observational study will be helpful for designing a subsequent randomized controlled trial.

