- Treatment : type of treatment, start date, PSA value before treatment; if surgery type of surgery and pathological TNM, margins, Gleason Score, number of positive lymph nodes; if external RT (intent, modality, technique, dose/fraction, volumes, concomitant hormonal therapies); if brachytherapy (type, intent, dose); if hormone therapy (type of drugs, start and end date, total duration);
- Acute and late toxicities;
- Biochemical Relapse with PSA value and date of last PSA;
- Quality of life and symptoms due to prostate cancer (Italian UCLA-PCI);
- General quality of life SF-12.

Toxicity and response evaluation

The enrolled patients will undergo the first follow up visit one month after the end of radiotherapy. On that occasion, clinical examination will be performed and previously prescribed blood tests, if required, will be evaluated. Genitourinary and gastrointestinal toxicity due to radiation therapy for prostate cancer will be reported according to the NCI Common Terminology Criteria for Adverse Events (CTCAE) version 4 for adverse event (AE) reporting. The CTCAE version 4 is identified and located on the CTEP web site at:

http://ctep.cancer.gov/protocolDevelopment/electronic_applications/ctc.htm [48]

In addition, a Case Report Form (CRF) will be completed (see Attachment 2), regarding:

- Technical characteristics of the radiation treatment (dose, volume, technique, association or not with hormonal therapy);
- Quality of life and complications due to prostate cancer (according to Italian UCLA-PCI) [45, 46];
- General quality of life (SF-12 Standard V1) [47].

Thereafter patients will be evaluated at 3-months, 6-months and 12-months after the end of radiotherapy, and then every 6 months for at least 24 months. During all those scheduled follow up visits, PSA level (jointly with testosterone, in case of association with hormonal therapy) and

previously prescribed blood texts if required, will be evaluated. Patients will undergo clinical examination, and genitourinary and gastrointestinal toxicity will be assessed according to the CTCAE v4.0 classification scale). In addition, a CRF (see Attachment 3) will be completed at each visit, regarding:

- Survival status (mortality, date and cause of death) or exit from the study;
- If macroscopical recurrence or disease progression occurred, the radiological exams (if performed);
- Further treatments received/planned after radiotherapy;
- The last available PSA;

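### For cause-specific survival, report cumulative incidence alongside the planned Kaplan-Meier curves; the overstatement of prostate-cancer mortality is small and the change is nearly free

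*Combined protocol and SAP*

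**What the plan says.** The body text lists the endpoints after overall survival (OS) as follows: "Secondary endpoints will be CSS, bRFS, gastrointestinal and genitourinary toxicity, QoL deterioration". The End-points entry of the synopsis agrees. Neither place defines CSS or bRFS, and neither says how a death without the event is handled.

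Under Statistical Analyses, and in the same words in the synopsis, the only estimator named is Kaplan-Meier: "In order to compare groups in terms of survival end-points, Kaplan-Meier curves will be estimated and log-rank tests will be performed". The adjusted analysis is described only in general terms: "regression models will be used for evaluating the associations of some variables with survival taking account of possible confounders". Cumulative incidence and competing risks are mentioned nowhere.

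The data for a competing-risk estimate are collected. The follow-up form records "Survival status (mortality, date and cause of death) or exit from the study", and the third aim is "To register prospectively biochemical and clinical failure, prostate cancer deaths and deaths for any cause in the population studied".

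Two uses of the results are stated under Aims of the study. The fifth aim is "To compare clinical outcomes and toxicities observed in the different clinical and therapeutic subgroups with the corresponding historical data", taken from existing AIRO databases. The sixth and seventh aims use the data to decide on and design a randomised trial.

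**The concern.** A man who dies of another cause can no longer die of prostate cancer. If his death is censored, Kaplan-Meier treats him as still at the same future risk as the men who remain. The complement of the curve (1-KM) then answers a hypothetical question: how many men would die of prostate cancer if no other cause of death existed. Read as the share of real patients who die of the disease, it is too high.

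This matters for the stated purpose. A later randomised trial has to be sized on events that will actually occur, and that calls for absolute risks. The same issue arises for bRFS if deaths without relapse are censored. There the missing definition also affects the historical comparison, because the two sides may not have counted death in the same way.

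**Working it through.** **The plan's own figure.** The only stated precision concerns OS: 0.8 at 5 years, 400 patients, 95% interval 0.76-0.84. The Wald interval is 0.8 ± 1.96 × √(0.8 × 0.2 / 400) = 0.8 ± 0.039, that is 0.761-0.839. It reproduces. No figure is stated for CSS.

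**Inputs.** The 5-year OS of 0.8 and N = 400 come from the Sample size section. Follow-up is at least 3 years per patient, with the last scheduled visit 36 months after radiotherapy, so the 3-year results are closest to what the study will observe. The documents give no split of deaths by cause; I assume a prostate-cancer share s of 25%, 50% or 75%, constant hazards and independent causes.

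**Formulas.** The total hazard is h = -ln(0.8)/5 = 0.0446 per year.
- Kaplan-Meier complement with other-cause deaths censored: 1-KM = 1 - exp(-s·h·t)
- Cumulative incidence: CIF = s × (1 - exp(-h·t))
- Approximate 95% half-width of 1-KM with complete follow-up: 1.96 × √(p(1-p)/400), where p = 1-KM

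| Years | Share s | 1-KM | CIF | Excess (points) | Half-width (points) |
|---|---|---|---|---|---|
| 3 | 25% | 3.29% | 3.13% | 0.16 | 1.7 |
| 3 | 50% | 6.48% | 6.27% | 0.21 | 2.4 |
| 3 | 75% | 9.55% | 9.40% | 0.16 | 2.9 |
| 5 | 25% | 5.43% | 5.00% | 0.43 | 2.2 |
| 5 | 50% | 10.56% | 10.00% | 0.56 | 3.0 |
| 5 | 75% | 15.41% | 15.00% | 0.41 | 3.5 |

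In relative terms the excess is about 2-5% at 3 years and 3-9% at 5 years. A simulation of 2000 cohorts of 400 (share 50%, censoring uniform between 3 and 5 years) gave mean excesses of 0.21 points at 3 years and 0.54 at 4.9 years.

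**Dependence on other-cause mortality.** Hold the prostate-cancer hazard fixed at 10% net mortality at 5 years (assumed) and vary net 5-year other-cause mortality (assumed). With hp and ho the two hazards, 1-KM = 1 - exp(-hp·t) and CIF = hp/(hp+ho) × (1 - exp(-(hp+ho)·t)).

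| Other-cause mortality, 5 years | 1-KM, 5 years | CIF, 5 years | Gap, 5 years (points) | Gap, 3 years (points) |
|---|---|---|---|---|
| 5% | 10.0% | 9.75% | 0.25 | 0.1 |
| 10% | 10.0% | 9.50% | 0.5 | 0.2 |
| 20% | 10.0% | 8.98% | 1.0 | 0.4 |
| 30% | 10.0% | 8.44% | 1.6 | 0.6 |
| 40% | 10.0% | 7.87% | 2.1 | 0.8 |

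The gap widens because the cumulative incidence falls. The Kaplan-Meier figure does not move.

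**bRFS: effect of the unstated rule.** This is an illustration with assumed net 5-year relapse of 30% and net death without relapse of 5% or 15%.
- Deaths censored: 1 - 0.70 = 30.0% failure at 5 years, and 1 - 0.70^0.6 = 19.3% at 3 years.
- Deaths counted as events, 5% mortality: 1 - 0.70 × 0.95 = 33.5% at 5 years, and 1 - (0.70 × 0.95)^0.6 = 21.7% at 3 years.
- Deaths counted as events, 15% mortality: 1 - 0.70 × 0.85 = 40.5% at 5 years, and 1 - (0.70 × 0.85)^0.6 = 26.8% at 3 years.

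The choice of rule moves the result by 2.4-7.5 points at 3 years and 3.5-10.5 points at 5 years under these assumptions.

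**The case against.** The strongest reply is that nothing planned is invalid. Under independent censoring 1-KM is a legitimate estimate of net risk, and the log-rank test is a valid comparison of cause-specific hazards. Regression adjustment is also planned, and OS, the primary endpoint, has no competing event. All of this stands. So does the point about size: the cohort-level excess is far smaller than the sampling error. It is also fair to say that the plan does not state that other-cause deaths are censored. That is the usual meaning of Kaplan-Meier for CSS, but here it is an inference from an undefined endpoint.

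A reader might infer two stronger claims, and the documents support neither.

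- One is that the study compares older or sicker subgroups, where the excess is largest. The comparisons named concern elective nodal irradiation, androgen deprivation, radical versus adjuvant setting, and clinical and therapeutic subgroups against historical data. Age and comorbidity are collected at baseline, but no comparison by either is specified. Treatment follows guidelines and each centre's own protocol, so other-cause mortality may differ between groups, but that is conjecture.
- The other is that part of a Kaplan-Meier difference between groups would reflect different other-cause mortality. Under independent hazards the reverse holds. In the second table, groups with 5% and 40% other-cause mortality have the same 1-KM, while their cumulative incidences differ by 1.9 points. Kaplan-Meier could be distorted between groups if the causes of death were dependent, but nothing in the documents lets that be assessed.

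What remains is the difference between net and actual risk when absolute figures are reported.

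**Conclusion.** The point holds as a free improvement to the reporting of secondary endpoints; it is not a flaw in the comparative analysis. With other-cause deaths censored, the CSS curves would overstate the actual probability of prostate-cancer death by about 0.2 points at 3 years and 0.4-0.6 points at 5 years. This rests on the plan's 5-year OS of 0.8, constant independent hazards and an assumed 25-75% share of prostate-cancer deaths. A gap of 1-2 points at 5 years needs other-cause mortality of roughly 20-40%, at an assumed 10% net prostate-cancer mortality; the documents do not give those levels for any group.

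For bRFS the missing definition matters more than the choice of estimator, but the size shown is illustrative because both rates are assumed.

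**What to change.** In Statistical Analyses and the matching synopsis entry:

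- Define CSS and bRFS, including how a death without the event is handled.
- Report the Aalen-Johansen cumulative incidence of prostate-cancer death and of other-cause death side by side, and name these as the absolute-risk estimates for planning the randomised trial. Showing both also lets a reader see when a difference in cumulative incidence comes from other-cause mortality.
- Keep log-rank or Cox as the comparison of cause-specific hazards, and keep Kaplan-Meier for OS.
- For bRFS, either count death as an event or report the cumulative incidence of relapse with death as a competing event. Apply the same rule to the historical AIRO data.

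The cost is a few sentences and a small amount of programming. Date and cause of death are already on the follow-up form, so no new data, visits or patients are needed. Applying one bRFS rule to the historical comparison does require that the AIRO databases record deaths without relapse; the documents do not say whether they do.
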